17.3. Modified International Working Group AML Response Criteria (Cheson, 2003)

Hematologic Response According to IWG Criteria for AML

Category	Definition
Morphologic Complete Remission (CR)	
 • BM Blasts < 5% 
AND
 
 • All of the following peripheral blood values met: 
 ○ Platelets $\geq 100 \times 10^9/L$ ○ ANC $\geq 1.0 \times 10^9/L$ 
Where the date of the hematology assessment used is within the window -8 and +8 days of BM date. If multiple hematology assessments within this window, the closest to BM date should be used. If multiple on same distance to BM date, the one before BM date should be used
 
AND
 
 • No platelet, or whole blood transfusions for 1 week (7days) prior to the date of the hematology assessment used for the response evaluation
Morphologic Complete Remission with Incomplete Blood Count Recovery (CRi)	
 ▪ BM Blasts < 5% 
AND
 
 ▪ One or both of the following peripheral blood values met: 
 ▪ Platelets < $100 \times 10^9/L$ ▪ ANC < $1.0 \times 10^9/L$ 
Where the date of the hematology assessment used is within the window -8 and +8 days of BM date. If multiple hematology assessments within this window, the closest to BM date should be used. If multiple on same distance to BM date, the one before BM date should be used

Category	Definition
Cytogenetic Complete Remission (CRc)	
 ▪ CR criteria met 
AND
 
 ▪ Abnormal karyotype present at baseline 
AND
 
Reversion to normal karyotype at time of CR (based on ≥ 10 metaphases), where date of cytogenetic sample = date of BM sample used for the CR assessment

Partial Remission (PR)	
 ▪ One of the following BM Blasts values met: 
 ▪ BM blasts of 5% to 25% (inclusive) when baseline BM blasts is 50% to 100% (inclusive) ▪ BM blasts $\geq 5\%$ and 50% decrease from baseline when baseline BM blasts is $\leq 49\%$ (inclusive) 
AND
 
 ▪ All of the following peripheral blood values met: 
 ▪ Platelets $\geq 100 \times 10^9/L$ ▪ ANC $\geq 1.0 \times 10^9/L$ 
Where the date of the hematology assessment used is within the window -8 and +8 days of BM date. If multiple hematology assessments within this window, the closest to BM date should be used. If multiple on same distance to BM date, the one before BM date should be used

Relapse after CR or CRi	
 ▪ $> 5\%$ blast in peripheral blood following CR or CRi 
OR
 
$> 15\%$ BM blast following CR or CRi

Treatment Failure	
 ▪ Death w/death date during Cycle 1 
OR
 
 • Death w/death date ≤ 28 days after last dose date and prior to C2D1

Category	Definition
Progressive Disease^b	
 ▪ If the lowest/best response %BM blast is $\leq 70\%$, PD is defined when there's an increase of %BM blast of at least 50%. 
If the lowest/best response %BM blast is $> 70\%$ instead, PD is defined when there's an increase of %BM blast of at least 10% (absolute increase). If %BM blast doesn't increase more than 10%, PD is defined as an increase of at least 2x in %PB blast from the lowest/best response with %PB blast $> 10\%$.

Stable disease	
 ▪ Any evaluable time point where criteria for all other response categories (i.e., CR, CRi, PR, PD, Treatment failure, Not Assessable) are not met

ANC = absolute neutrophil count

^a If the pretreatment bone marrow blast percentage was 50% to 100%, the percentage of blasts must decrease to a value between 5% and 25%; if the pretreatment blast percentage was 20% to less than 49%, they must decrease by at least half to a value of more than 5%.

^b Modification to IWG response criteria.

Notes: Deletions to the IWG response criteria are not shown.

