## Appendix K: Modified International Working Group AML Response Criteria (Cheson, 2003)

### Hematologic Response According to IWG Criteria for AML

Category	Definition
Morphologic Complete Remission (CR)	The following conditions should be met: 
 
ANC <math>\geq</math> 1,000/<math>\mu</math>Lb;
 
Platelet count <math>\geq</math> 100,000/<math>\mu</math>L;
 
The bone marrow should contain less than 5% blast cells;
 
Auer rods should not be detectable;
 
Independent of transfusions
 

Morphologic Complete Remission with Incomplete Blood Count Recovery (CRi)	Defined as a morphologic complete remission but the ANC count may be < 1,000/ $\mu$ L and/or the platelet count may be < 100,000/ $\mu$ L.
Cytogenetic Complete Remission (CRc)	Defined as morphologic complete remission with a reversion to a normal karyotype.
Partial Remission (PR)	Defined as an ANC $\geq$ 1,000/ $\mu$ L and platelet count $\geq$ 100,000/ $\mu$ L with a > 50% decrease in the percentage of bone marrow blasts to 5% to 25% (a blast count value of $\leq$ 5% may also be considered a partial remission if Auer rods are present). a, b
Relapse after CR or CRi	Defined as 1) the reappearance of > 5% blasts in the peripheral blood, or 2) a single finding of > 15% blasts in the bone marrow. All of the above occurrences should be attributed to relapse following CR or CRi and not attributable to another cause (eg, bone marrow regeneration after consolidation therapy) b .
Treatment Failure	Aplasia: Subject survives $\geq$ 7 days post chemotherapy; death while cytopenic, with aplastic bone marrow. Indeterminate Cause: 
 
Subjects who die < 7 days posttherapy
 
Subjects who die <math>\geq</math> 7 days posttherapy with no peripheral blood blasts, but no bone marrow examinationb
 
Subjects who die without completing the first course of therapy
 

Category	Definition

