4.3.2. AML Cohort

Studies conducted by Dombret et al and Fenaux et al ([Dombret, 2015](#); [Fenaux, 2010](#)) showed a response (CR + complete remission with incomplete blood recovery [CRi]) rate of 25% in AML subjects treated with azacitidine. Assuming a treatment effect of 100% relative improvement of CR and CRi (from 25% to 50% absolute CR and CRi rates), a sample size of 110 subjects will provide a power of 80% to detect such an effect at the 5% level of statistical significance.

An interim analysis for futility purpose will be conducted on the first 50 subjects who have completed 6 cycles of treatment unless they have established an earlier response (CR or CRi) or discontinued due to death or disease progression. Subjects assigned to Arm A, who received less than 3 cycles of durvalumab and continued under azacitidine monotherapy are to be excluded from the interim analysis.

The AML cohort will continue to enroll a total of 110 AML subjects if one of the below conditions is met at the interim analysis:

- If the ORR (considering the composite score of CR + CRi) in the combination arm is numerically higher than or equal to the control group (azacitidine alone) or,
- If the response rate of one of the components of this composite score (in particular CR rate) in the combination arm is numerically higher than or equal to the control group (azacitidine alone) or,
- If evidence of a clinical meaningful difference in favor of the combination arm in a secondary endpoint (eg, duration of response) is provided.

Durvalumab (MEDI4736)

Statistical Analysis Plan: Protocol MEDI4736-MDS-001 _____ Celgene Corporation

If none of these conditions are met, then the cohort might be terminated. The DMC will review the data at the time of interim analysis and will provide recommendation/advice to Celgene.

CELGENE PROPRIETARY INFORMATION

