10.1. Primary Efficacy Endpoint

The primary efficacy endpoint is the ORR and will be programmatically derived using the results/assessments generated by the central morphologic/cytogenetic and hematology laboratories. In case no central hematology results are available within +/- 8 days of bone marrow samples, local hematology results might be used if available. This analysis will be conducted after completion of the Stage 1 and Stage 2 portions of the study. A subject is considered evaluable for response if they have undergone at least one disease status assessment following treatment Cycle 6. Subjects who discontinue from the treatment phase before the first post baseline efficacy assessment (following treatment Cycle 3) will be replaced unless the subject had a documented progression of their disease or died and will be considered as non-responders. If one post baseline disease assessment is performed, this assessment would be considered for response.

The difference of the proportions for overall response between the azacitidine alone and combination therapy arms will be tested using a standard Wald asymptotic two-sided test with unpooled estimate of variance and presented along with corresponding two-sided 95% CIs.

The hypothesis tested will be:

$$H_0: d = 0$$

versus

$$H_a: d \neq 0,$$

Where $d = p_1 - p_2$ is difference in overall response rate in the combination therapy arm (p_1) versus the overall response rate in the monotherapy arm (p_2).

The test statistic is

$$z = \hat{d}/se(\hat{d})$$

Where, the standard error is computed from the sample proportions as

$$se(\hat{d}) = \sqrt{\frac{\hat{p}_1(1 - \hat{p}_1)}{n_1} + \frac{\hat{p}_2(1 - \hat{p}_2)}{n_2}}$$

Where \hat{p}_1 (respectively \hat{p}_2) is the estimated response rate in the combination therapy arm (respectively monotherapy arm) and is derived as the observed response rates in respective arms.

Myelodysplastic Syndromes Cohort

For the MDS cohort, the primary efficacy endpoint is the proportion of subjects achieving an overall response rate (defined as CR, PR, mCR, and/or HI) as determined using the International Working Group (IWG) 2006 response criteria for MDS ([Appendix 17.2](#)). The ORR will be summarized together with two-sided 95% CI. Subjects discontinued before 6-cycle treatment without achieving overall response will be counted as nonresponders.

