The number and percentage of subjects who achieve each component of the overall response (CR, PR, mCR, HI-E, HI-P, HI-N) will be summarized together with associated two-sided 95% CI.

The best overall response per IWG 2006 response criteria will be summarized. The best overall response is defined as the best response prior to progressive disease and first subsequent therapy.

The below order will be considered for the definition of best response:

1. CR
2. PR
3. mCR
4. SD
5. PD
6. Disease transformation
7. Failure due to death
8. Not Evaluable/Missing

Acute Myeloid Leukemia Cohort

For the AML cohort, the primary efficacy endpoint is the proportion of subjects achieving an overall response rate (CR or CRi) based on modified IWG 2003 response criteria for AML ([Appendix 17.3](#)). The ORR will be summarized together with two-sided 95% CI. Subjects discontinued before 6-cycle treatment without achieving overall response will be counted as nonresponders.

The number and percentage of subjects who achieve CR, PR, CRi, HI-E, HI-P and HI-N will be summarized together with associated two-sided 95% CI

The best overall response per modified IWG response criteria will be summarized. The best overall response is defined as the best response prior to progressive disease and first subsequent therapy.

The below order will be considered for the definition of best response:

1. CR
2. CRi
3. CRc

4. PR
5. SD
6. PD
7. Treatment failure
8. Not Evaluable/Missing

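### SAP 17.3 leaves one AML marrow remission unclassified: recovered counts plus a recent platelet or whole-blood transfusion default to stable disease, while a lower count gives CRi

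*SAP*

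**What the plan says.** SAP 10.1 makes CR or CRi the AML primary endpoint and says that it "will be programmatically derived using the results/assessments generated by the central morphologic/cytogenetic and hematology laboratories". The wording of the response table therefore decides each subject's outcome.

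The relevant rows of SAP 17.3 are:

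- **CR:** marrow blasts below 5%, platelets at least 100 × 10⁹/L, ANC at least 1.0 × 10⁹/L, and "No platelet, or whole blood transfusions for 1 week (7days) prior to the date of the hematology assessment used".
- **CRi:** marrow blasts below 5% and "One or both of the following peripheral blood values met", the values being platelets below 100 and ANC below 1.0. There is no transfusion condition.
- **PR:** marrow blasts of at least 5%, with both counts recovered.
- **Stable disease:** "Any evaluable time point where criteria for all other response categories" are not met.

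Protocol Appendix K has two further features. Its CR row includes "Auer rods should not be detectable" and "Independent of transfusions", the latter with no product and no time window. Its CRi row describes a morphologic complete remission in which the counts are permitted to be low.

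SAP 15 states in general terms that response derivations were updated for consistency with the IWG criteria. It mentions neither Auer rods nor the transfusion window.

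**The concern.** The CR and CRi rows should between them settle every marrow with blasts below 5%, and they do not. CR carries a transfusion condition and CRi does not, and the SAP turns counts that may be low in the protocol's CRi into counts that must be low. A recently transfused subject whose counts have recovered falls between the two rows.

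The result runs the wrong way: with the transfusion held fixed, a higher platelet count turns a responder into a non-responder on the primary endpoint. Time to response, duration of response and relapse-free survival start from the same derived response and inherit the problem.

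The departures from Appendix K matter separately. Without the Auer-rod condition, a low-blast marrow with Auer rods becomes CR or CRi, whereas Appendix K denies it CR and allows it to be called PR, which is not an AML response for ORR. Limiting the transfusion condition to platelets and whole blood means that packed red cells no longer block CR. That moves the CR rate, which the futility rule in SAP 4.3.2 singles out.

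**Working it through.** **Classification check.** Apply the SAP 17.3 rows to a marrow with 3% blasts (an illustrative value below 5%), with counts just below or at each threshold. Transfusion means platelets or whole blood in the 7 days before the hematology assessment. It is assumed that neither progression nor treatment failure applies.

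| Platelets (×10⁹/L) | ANC (×10⁹/L) | No transfusion | Transfusion |
|---|---|---|---|
| 99 | 0.9 | CRi | CRi |
| 99 | 1.0 | CRi | CRi |
| 100 | 0.9 | CRi | CRi |
| 100 | 1.0 | CR | **Stable disease** |

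Seven of the eight cells are responses. In the exception, CR fails on the transfusion, CRi fails because neither count is low, PR fails because blasts are below 5%, and the stable-disease row takes the remainder. All three other transfused cells are CRi, so the SAP is not excluding transfused subjects on principle.

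The MDS table in SAP 17.2 handles a similar situation explicitly: a CR whose counts are not confirmed for 28 days is assigned to marrow CR. The AML table has no such fallback.

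**Plan's own figure.** SAP 4.3.2 gives 110 subjects for 80% power, 25% versus 50%, at the 5% level. With the SAP's two-sided test and unpooled variance:

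n per arm = (1.960 + 0.842)² × (0.25 × 0.75 + 0.50 × 0.50) / 0.25² = 7.849 × 0.4375 / 0.0625 = 54.9, rounded up to 55, or 110 in total, with power 80.0%. The figure reproduces.

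**Size per subject.** With 1:1 allocation, 110/2 = 55 per arm and 50/2 = 25 per arm at the interim. One subject moves an arm's rate by 1/55 = 1.8 points, or by about 1/25 = 4 points at the interim.

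**Illustrative range, by assumption only.** The documents do not say how often the cell occurs. Suppose the planning rates count these cases as responses and the same share of responders is lost in both arms:

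| Share lost (assumed) | Rates | Power at 55 per arm | N for 80% power |
|---|---|---|---|
| 5% | 23.75% vs 47.5% | 76.6% | 120 |
| 10% | 22.5% vs 45% | 72.9% | 132 |
| 20% | 20% vs 40% | 65.0% | 158 |

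These rows show the direction of the effect. They do not estimate its size.

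**The case against.** Several stronger readings are tempting, and the case against them is good.

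- **That the SAP scores true remissions as non-response.** Appendix K makes transfusion independence part of CR, and its CRi relaxes only the counts. Read strictly, it also denies this subject both categories. This stands. The defect is the SAP's internal inconsistency, not a clear departure from a protocol-defined response.
- **That two protocol CR criteria are dropped.** Only the Auer-rod condition is. The transfusion condition survives as the 7-day platelet and whole-blood rule, and Appendix K never names red cells. It is narrowed, not omitted.
- **That the red-cell change alters ORR.** A subject given packed red cells, with recovered counts, is CR under the SAP and would be CRi under the fix below. Between those two, ORR is unchanged and only the CR/CRi split moves.
- **That each affected subject is lost.** Stable disease is assigned per time point. Protocol 6.7.3 schedules response assessment after every third cycle and at treatment discontinuation, and SAP 10.1 takes the best response before progression or subsequent therapy. One qualifying assessment rescues the subject, so 1.8 and 4 points are upper bounds.
- **That the interim could be decided by this.** The futility conditions are alternatives, and failing all of them means only that the cohort might be terminated on DMC advice.

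Two mitigations are weaker. SAP 10.2 also reports ORR by investigator assessment, which would expose discrepancies but does not correct the primary analysis. The note that deletions from the IWG criteria are not shown stands in both documents, so it cannot explain a difference between them.

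None of this removes the reversal between platelets of 99 and 100.

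**Conclusion.** The SAP is wrong as written on one cell of the AML table. Blasts below 5%, platelets of at least 100, ANC of at least 1.0 and a platelet or whole-blood transfusion in the prior 7 days give stable disease, while a lower count gives CRi. This follows from the rule text and needs no assumption about frequency. The Auer-rod omission and the narrowed transfusion condition are also real, and neither is specifically declared.

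The effect on the trial is not known. The per-subject figures are ceilings that assume equal arms and a subject with no qualifying assessment elsewhere. The number of such subjects may be small or nil. A reader might infer that 110 subjects is too few; the documents do not support that, since the calculation reproduces and any power loss rests wholly on an assumed frequency. The point should be corrected because the rule is incoherent on a programmed primary endpoint and the repair is cheap.

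**What to change.** Before database lock, and without reference to responses by arm:

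1. Assign the uncovered case explicitly in SAP 17.3. Defining CRi as marrow blasts below 5% with any CR count or transfusion condition not met agrees with the SAP's existing treatment of transfused subjects with low counts. It is broader than Appendix K's CRi, so SAP 15 should declare it as a departure and note that it can only raise ORR for these cases. Applying the transfusion condition to CRi as well would also be coherent, but would remove subjects now counted as CRi.
2. Restore the Auer-rod condition where the finding is reported, or declare its removal in SAP 15.
3. Reconcile the transfusion condition for CR with Appendix K by stating whether packed red cells count, or declare the narrowing in SAP 15.

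The cost is a few lines in SAP 17.3 and 15 and a small change to the derivation program. If red cells are added to the CR condition, the CR rate may fall slightly with ORR unchanged under item 1. Restoring the Auer-rod condition can only remove responders.

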5.1.3. Calculation of Cycles

The start date of each treatment cycle will be calculated based on study drug exposure records for each subject. The start date of the first cycle will be the date when the subject receives any dose of study drug. First dose date of Durvalumab infusion or azacitidine injection in each cycle will be considered as the start of the cycle.

Once the start dates, eg, $S_1, S_2, S_3 \dots$ are calculated, the end date of each cycle is calculated as the day before the start date of the following cycle, ie, $E_i = S_{i+1} - 1$. The last cycle in the treatment

phase is defined as the cycle with the last dose of any study drug. For the last cycle, the end date will be the last dose date plus 28 days or the death date, whichever is earlier.

The cycle number for each date of interest, eg, AE or lab, will be calculated based on the cycle window set by their start and end dates. If a date is on or after S_i and before S_{i+1} , the corresponding cycle number will be i .

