15. CHANGES TO THE STATISTICAL ANALYSES SECTION OF THE PROTOCOL

Response derivations have been updated for consistency with IWG Response Criteria in Myelodysplasia (Cheson, 2006) and Modified IWG AML Response Criteria (Cheson, 2003).

IA requirements and definition of EE population have been detailed in order to specify that subjects assigned to Arm A, who received less than 3 cycles of durvalumab and continued under azacitidine monotherapy are to be excluded from interim analysis and/or in the EE population.

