17.2. International Working Group (IWG) Response Criteria in Myelodysplasia (Cheson, 2006)

Altering Disease Natural History	
Complete remission (CR)	
 ▪ BM Blasts \leq 5% 
AND
 
 ▪ All of the following peripheral blood values met: 
 ▪ Hemoglobin \geq 11 g/dL ▪ Platelets \geq 100 x10⁹/L ▪ ANC \geq 1.0 x10⁹/L ▪ Peripheral Blasts=0% 
Labs must meet criterion for at least 28 consecutive days. If not confirmed for 28 days then response should be mCR.
 
In addition
 
 ▪ The 7/3 rule should be applied to Hemoglobin. ▪ Platelets collected 3 days period following Platelet transfusion will not be used - ANC values that must be at least 14 days following a G-CSF application
Partial remission (PR)	
 ▪ BM Blasts decreased by \geq 50% over pretreatment but still $>$ 5% 
AND
 
 ▪ All of the following peripheral blood values met: 
 ▪ Hemoglobin \geq 11 g/dL ▪ Platelets \geq 100 x10⁹/L ▪ ANC \geq 1.0 x10⁹/L ▪ Peripheral Blasts=0% 
Labs Must meet criterion for at least 28 consecutive days.
 
In addition
 
 ▪ The 7/3 rule should be applied to Hemoglobin. ▪ Platelets collected 3 days period following Platelet transfusion will not be used 
ANC values that must be at least 14 days following a G-CSF application

Marrow CR	
 ▪ Bone marrow: $\leq 5\%$ myeloblasts and decrease by $\geq 50\%$ over pretreatment with baseline BM blast $>5\%$ 
AND
 
 ▪ Not all of the following peripheral blood values met or none are met: 
 ▪ Hemoglobin ≥ 11 g/dL ▪ Platelets $\geq 100 \times 10^9/L$ ▪ ANC $\geq 1.0 \times 10^9/L$ ▪ Peripheral Blasts=0% 
Peripheral blood: if HI responses, they will be noted in addition to marrow CR

Stable disease (SD)	Any evaluable time point where criteria for all other response categories (i.e., CR, PR, PD, Failure due to death, Not Assessable) are not met
Failure	Death during treatment

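### SAP 17.3 closes AML Treatment Failure at Cycle 2 Day 1, so later deaths without a post-baseline marrow can only be labelled not evaluable or missing in the best-response table

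*SAP*

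**What the plan says.** The AML Treatment Failure row in SAP 17.3 has two limbs. The first is "Death w/death date during Cycle 1". The second is a death no later than "28 days after last dose date and prior to C2D1". SAP 5.1.3 ends a cycle the day before the next one starts; if there is no next cycle, "For the last cycle, the end date will be the last dose date plus 28 days or the death date, whichever is earlier". Both limbs therefore close once Cycle 2 begins.

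SAP 10.1 ranks AML best response as CR, CRi, CRc, PR, SD, PD, Treatment Failure and finally "8. Not Evaluable/Missing". No other rank refers to death.

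Protocol Appendix K is wider. Its Treatment Failure entry includes deaths in aplasia and deaths at or beyond "7 days posttherapy with no peripheral blood blasts, but no bone marrow examination". Neither is tied to Cycle 1.

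For the MDS cohort, SAP 17.2 defines Failure simply as "Death during treatment".

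On departures from the protocol, SAP section 15 states: "Response derivations have been updated for consistency with IWG Response Criteria in Myelodysplasia" and the modified AML criteria. It gives no row-level detail.

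**The concern.** A death on treatment is an outcome. A subject with no assessment is a gap in the data. The AML rule puts some of the first kind into the second. The same death in Cycle 2 or 3 would be a failure in the MDS table and missing in the AML table, and for some of these deaths the AML label also departs from the protocol's definition. The table is presented by arm, so if Cycle 2–3 deaths were more frequent in one arm, that table would show the difference as missing data. At stake is the correct reading of one planned descriptive efficacy table.

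**Working it through.** **Step 1: which category can such a subject enter?** Take an AML subject who dies after Cycle 2 Day 1 with no post-baseline marrow.

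- CR, CRi, CRc and PR in SAP 17.3 each need a post-baseline marrow blast value: not met.
- SD needs an evaluable time point: not met.
- PD is anchored on the lowest or best marrow blast percentage. Its peripheral-blood limb is reached only through the marrow limb: not met.
- Treatment Failure closed at Cycle 2 Day 1: not met.
- What remains is the last rank. The SAP does not say this outright; it follows by elimination.

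The first scheduled on-treatment marrow is Cycle 3 Day 22, which is Day 2 × 28 + 22 = 78, or at the latest before Cycle 4, about Day 3 × 28 = 84 (Protocol section 5, marrow footnote). Deaths between the end of Cycle 1 and Day 78–84 are the ones exposed.

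**Step 2: the denominator.** The plan's 110 reproduces. With 25% versus 50%, two-sided 5%, 80% power and unpooled variance:

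n per arm = (1.960 + 0.842)² × (0.25 × 0.75 + 0.50 × 0.50) / 0.25² = 54.9, so 55 per arm and 110 in total.

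**Step 3: how many subjects?** The documents give no figure, so this rests on assumptions.

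Inputs:
- median OS on azacitidine in AML of 10.4 months, 95% CI 8.0 to 12.7 (Protocol 1.3.3);
- 30.4375 days per month (SAP 5.1.2);
- end of Cycle 1 at Day 28 (on schedule), Day 35 (Cycle 2 never given: last dose Day 7 + 28) or Day 42 (a 14-day delay; Protocol 3.2.2 permits delays of up to 42 days).

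Assumed survival model, Weibull with shape k: F(t) = 1 − exp(−λtᵏ), where λ = ln 2 / Mᵏ and M = 10.4 × 30.4375 = 316.55 days. Shape k = 1 is a constant hazard; smaller k puts more deaths early.

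Worked case, k = 1: λ = 0.6931 / 316.55 = 0.00219 per day. F(28) = 0.0595 and F(84) = 0.1680. The difference is 0.1085 × 110 = 11.9 subjects, and the share of deaths by Day 84 is 0.1085 / 0.1680 = 65%.

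Deaths per 110 after Cycle 1 ends, to Day 78 / to Day 84, with the share of all deaths by Day 84 in brackets:

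| Shape k | Cycle 1 ends Day 28 | Day 35 | Day 42 |
|---|---|---|---|
| 1.0 | 10.7 / 11.9 (65%) | 9.2 / 10.4 (56%) | 7.6 / 8.8 (48%) |
| 0.7 | 12.1 / 13.2 (50%) | 10.0 / 11.2 (42%) | 8.1 / 9.3 (35%) |
| 0.5 | 11.5 / 12.5 (38%) | 9.4 / 10.4 (31%) | 7.5 / 8.5 (26%) |

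The count runs from 7.5 to 13.2. Repeating the grid at medians of 8.0 and 12.7 months widens it to 6.4 to 15.3, with shares of about 25% to 65%. The share depends heavily on hazard shape and on the end of Cycle 1; the count much less so.

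The grid keeps the marrow date fixed. If a 14-day delay moves both ends (Day 42 to Day 98), the constant-hazard count is 110 × (exp(−0.0920) − exp(−0.2146)) = 11.6, inside the range.

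**Step 4: effect on the primary analysis.** SAP 10.1 counts AML subjects who stop before six cycles without a response as nonresponders, and the ITT population holds all randomized subjects. Relabelling these deaths moves no one between responder and nonresponder, so ORR, its test and the power in Step 2 do not change.

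**The case against.** The best defence is that little is lost. SAP section 12 reports all deaths, on- and off-treatment deaths with causes, Grade 5 TEAEs and a listing of subjects who died. OS is compared by stratified log-rank test. SAP 10.2 adds a best-response summary by investigator assessment, and the protocol has sites apply Appendix K. The affected subjects keep a visible row and stay in the ITT denominator. The two cohorts use different response criteria by design, and section 15 does say that derivations were updated.

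Most of this stands, and it rules out two stronger readings that a reader might draw. One is that the rule hides a mortality excess: it does not, because an excess would show in the death summaries, the Grade 5 tables and OS. The other is that most early deaths drop out of the table: no one drops out, and whether the share exceeds one half depends on assumptions. It falls below half once the Weibull shape is under about 0.7 (Cycle 1 ending Day 28) or 0.85 (Day 35).

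The defence does not rescue the label. Death summaries use the Safety Population and best response uses ITT, and no planned table links them, so the tables alone do not show which missing subjects had died. The on-treatment death window in SAP 12.1 also differs by drug: 90 days after durvalumab, 28 after azacitidine. Different criteria for two diseases do not explain a row narrower than the protocol's own AML definition.

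**Conclusion.** The point holds, with minor severity. As written, the AML rule mislabels deaths after Cycle 2 starts when there is no post-baseline marrow. It departs from Appendix K without saying so and disagrees with the MDS row.

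At the cited 10.4-month median, roughly 7 to 13 of 110 subjects could be affected, and about 6 to 15 across medians of 8.0 to 12.7 months. These are upper figures: the protocol calls for a marrow at treatment discontinuation and allows unscheduled ones, which will make some subjects evaluable. They also assume that survival in this trial resembles that of the cited azacitidine arm.

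The consequence is confined to labels in one descriptive table. The documents do not support a claim that deaths go unreported or that any efficacy conclusion changes.

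**What to change.** In SAP 17.3, remove the Cycle 1 and Cycle 2 Day 1 limits so that AML Treatment Failure follows Appendix K. That alone would leave out deaths with circulating blasts and no marrow, so add a best-response row to SAP 10.1 for death before the first response assessment, covering the remaining deaths without an evaluable assessment. State one time window for that row and apply it identically in both arms; the drug-specific windows in SAP 12.1 would not do this. Keep the last rank for subjects without an assessment who did not die in that window. Name the change in SAP section 15.

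The cost is a few lines of SAP text and one derivation. No new data are needed, and sample size and the primary analysis stay as they are.
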